**SHARE-D: a Decision Tool to Help Patients
Make Informed Lifestyle Choices**

NCT03276546

07 March 2016

Purpose and relevance

This project will inform development of a definitive shared decision tool and methods for its use in practice (eg. mobile application, with/without health professional). Further, it will be sustainable beyond the grant's lifetime as it will inform the design of a RCT and increase awareness of peoples' needs and resources in supporting lifestyle change.

To our knowledge the tool which we propose to test, is novel. It is paper-based in its current format, designed to be carried out in consultation with a health professional, focuses on PA and diet, and considers individuals' personal circumstances. Our tool ('SHARE-D') aims to help people consider why and how they may change their lifestyles by guiding their decisions and taking account of their personal circumstances. Good decision-making, identifying the means of developing habits and routines, is the first step in the process of sustaining long-term change and healthy lifestyles. A novel instrument, targeting individuals with, and at risk of, chronic disease, to improve their decision-making through shared decision-making interventions thus has the potential to improve public health measurably.

Study aims and objectives

This feasibility study aims to examine the use of a questionnaire tool ('SHARE-D') for shared decision-making in primary care practice for patients with, and at high risk of, coronary heart disease (CHD), using both quantitative and qualitative methods. The project has six key objectives:

1. To test the feasibility of using a novel shared decision tool for diet and PA behaviour change, for patients in primary care.
2. To assess participants' diet and physical activity behaviour by administering the Dietary Instrument for Nutrition Education (DINE) questionnaire and Recent Physical Activity Questionnaire (RPAQ).
3. To make an objective assessment of participants' level of PA by using an accelerometer.
4. To explore patients' views regarding the usefulness and acceptability of the decision tool.
5. To explore practitioners' views of the decision tool.
6. To refine the design of a decision tool, for shared decision-making and for use in clinical practice, to facilitate initiation of sustained behaviour change.

Methods

Selection of practices

We propose to invite five general practices in Northern Ireland (NI) to participate, one from each of the five regional Health and Social Care Trusts. Practices will be selected purposively to include a range of geographical locations (rural/urban, with varying levels of socio-economic deprivation and social contexts) and practice size. With the assistance of the NI Clinical Research Network (Primary Care), we will telephone a key staff member in each of the selected practices to explain what the proposed study is about and explore their interest in participating. For those who express interest, we will post study information to the practice, allowing them time to discuss the study and decide whether to take part or if more information is needed. With their agreement, the researcher will arrange a suitable time to visit the practice and explain further the planned protocol. If an invited practice declines to participate we will identify a further practice with a similar profile for invitation to ensure that 5 practices participate.

Selection of patients

We propose to ask GPs to identify eligible patients (see *criteria below*) from their medical records or opportunistically and invite participation from people with a range of ages (18 years and above), different genders and, for those with established CHD, a range of time since diagnosis. We will ask GPs to identify 12 patients in each practice for invitation to take part in the study and to exclude from invitation patients whom they deem are physically or mentally unable to answer the proposed questionnaires, those who would be unable to make lifestyle changes because of physical or mental limitations and those who do not live freely within the community. It is anticipated that five or six invitees will agree to take part and include a range of possible co-morbidities and characteristics of interest. We recognise that GPs may choose to invite those whom they consider most likely to participate and to be compliant with the study protocol, thus introducing a possible risk of selection bias. However, we consider that the inclusion criteria will identify patients for whom the tool has relevance and they will have valuable contributions to make to the study findings. Moreover, possible factors influencing GPs' selection of patients will be sought through their participation in focus groups which will explore their perceptions of the applicability of the tool to a wider population than that included in the study sample.

Inclusion/exclusion criteria

Participants will have a Body Mass Index (BMI) greater than 30, indicating obesity, or low levels of physical activity (assessed by their general practitioner (GP), using the General Practice Physical Activity Questionnaire (GPPAQ), a tool recommended for use in primary care). We will include patients who have been diagnosed as having CHD and patients without a diagnosis of CHD but who are at high risk of CVD (10-year estimated risk of at least 20%, as assessed by the GP). Thus, our sample will include patients who would most benefit from behaviour change. Exclusion criteria, as listed above, are based on limitations in using the 'SHARE-D' tool in its current format or in making diet or PA change.

Sample size

As a feasibility study is planned, a formal sample size calculation has not been conducted. We plan to interview five patients from five practices (expecting less than 50% response from invitees in each practice) giving a total study sample size of 25. This size of sample will allow inclusion of patients with a range of conditions, socio-economic characteristics and community support. Selecting a practice from each of five different health and social care trusts allows inclusion of patients who have access to different models of health and social care provision of services to support healthy lifestyles.

Recruitment of patients

The researcher will provide a study invitation letter for the lead GP from each practice to, if he/she approves the content, send to selected patients with a study information sheet, reply slip and stamped addressed envelope so that patients will be encouraged to return the reply slip, indicating their decision about taking part in the study, to the practice. Those who agree to participate will, with their consent, be telephoned by the researcher to arrange a mutually convenient time and location for a meeting at which the researcher will explain the study fully and ask the patient to sign a consent form if they still agree to participate. They will have the opportunity to ask any questions about the study and will be assured of confidentiality.

Data collection

With consent, at their initial meeting, participants will complete the DINE (Roe et al, 1994) and RPAQ (Besson et al, 2010) questionnaires, administered by the researcher, a post-doctoral fellow with experience in working with patients with coronary heart disease, to provide a baseline measure of diet fat and fibre intake and a measurement of physical activity. Then, in consultation with a health professional in the practice (nurse or general practitioner), they will complete a decision tool, a paper-based questionnaire which will highlight the need for personal decisions regarding lifestyle behaviour. Based on current evidence, relating to factors known to be important in behaviour change, this tool will provide information about benefits and risks associated with diet and physical activity and will include a series of questions to encourage individuals to consider their personal lifestyle behaviours and how to make changes. Based on a review of theories of behaviour change, with a focus on health beliefs, social support and self-determination, this will facilitate their consideration of their own beliefs, attitudes and values, as well as conditions existing within their social and physical environments, which would support or hinder possible changes in their behaviour. The duration of the meeting and data relating to their age, gender, medical conditions, medication and social circumstances will also be recorded. Participants will be offered some Northern Ireland Chest, Heart & Stroke literature/leaflets outlining the importance of healthy lifestyles and they may keep these and refer to them at their convenience.

The decision tool to be tested is designed to encourage conversation between a patient and health professional and support shared decision-making. It allows opportunities for the patient to ask questions at any time. After a shared decision has been made regarding possible changes in diet and physical activity, the researcher will arrange contact again for one month later.

At the end of the initial meeting participants will be invited to wear an Actigraph GT3X accelerometer for a 7 day period, to provide an objective measure of their physical activity. If they agree to do so, arrangements will be made to collect the device at the end of this period. We have considered the risk of potential confounding effects on behaviour change of using an accelerometer (reactivity effects) but concluded that these would be outweighed by the additional information gained through testing the feasibility of its use. In a definitive study it would be valuable to include an objective measure to assess the impact of the intervention on physical activity behaviour change.

Follow-up contact

At a one month follow-up meeting the researcher will ask about progress in lifestyle change, repeat the DINE and RPAQ questionnaires, consider and record possible unmet needs for support in change, help participants to identify appropriate sources of support, provide 'signposting' to these and answer any queries. A written record will be made of whether they have been in contact with their GP or practice nurse or have received any support from health professionals, community based organisations/facilities or friends and family, relating to lifestyle change. At the completion of this meeting the researcher and participant will agree arrangements for contact to be made again, two months later.

At 3 months after the initial meeting, the researcher will again meet participants to repeat the DINE and RPAQ questionnaires and record unmet and met needs for support, with particular note of the availability and use of health service and community resources in supporting lifestyle behaviour change. Following a semi-structured interview approach, participants' views of the decision-making tool will be sought and noted in writing by the researcher. Questions will be asked about each section, and each question, in relation to usefulness, clarity and relevance regarding helping them to adopt and sustain healthy lifestyles. Opinions will be sought regarding possible different or preferred methods of its administration (eg. mobile application, with/without health professional). Responses will not be audiotaped in order to minimize possible inhibition of expression of frank opinion, since there is recognition that people who attempt to make lifestyle changes and do not succeed may be embarrassed by their lack of success and sensitive about an ongoing need to make changes. Also at this 3-month meeting patients will be again invited to wear an accelerometer for a 7-day period to record physical activity.

Semi-structured interviews with health professionals

After patients' interviews and questionnaires have been completed in all five practices and their views on the decision tool have been explored, interviews will be conducted in each practice with GPs who invited patients' participation and health professionals with whom the patients have consulted during the time of the study. We hope to recruit at least one GP or one practice nurse per practice. If more than two health professionals in a practice wish to participate then we would attempt to conduct a focus group in that practice. The aim of the focus groups is to ascertain if the patients have shared any information relating to their use of the decision tool in consultations and the views of GPs and nurses regarding its potential utility in everyday practice. This will include their opinions on how the tool could be used during a consultation, the types of patients for whom the use of the tool would be considered appropriate, the questions included in it and what could be included in a potential electronic application of the decision tool. Primary questions for these groups will also be informed by analysis of the patients' interviews. The interviews or focus groups with health professionals will be audio-taped, with consent, and the recorded data will be transcribed verbatim, anonymously, for analysis.

Data analysis

The lifestyle questionnaires DINE, to ascertain diet habits, and RPAQ, to measure physical activity, will be used in order to record a measure of these aspects of participants' lifestyles during the time of the study, in order to provide objective contextual detail for the qualitative findings. Comparisons will be made of DINE fibre, fat and unsaturated fat scores and of RPAQ scores between the baseline measurements and at one month and at 3 months, so that change may be tracked for individuals. Descriptive statistics will be reported only. These data will guide in sample size estimations for a later study. Data derived from the accelerometers (minutes of moderate and vigorous physical activity), at baseline and at the 3-month follow-up point, will provide an objective measure of physical activity. Qualitative analysis of patients' opinions of the decision tool and reasons for any behaviour change undertaken during the study, which will have been noted in writing by the researcher at the second and third meetings, will be carried out. Experiences of incentives and barriers to lifestyle behaviour change will be sought. Data collection and analysis will be iterative. Thematic analysis will be employed, using the constant comparative method and the support of the computer software programme NVivo (QSR, 2010). Focus groups and interviews with health professionals at the five practices will be analysed qualitatively using a theoretical framework analysis. All data will be recorded anonymously and no individual will be identified in any report of the study.

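### Does the plan need to name the SDs, correlations and intervals that the later trial's sample size will use?

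*Combined protocol and SAP*

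**What the plan says.** The Purpose and relevance section states the long-term aim: "it will inform the design of a RCT". The Data analysis section plans to compare three DINE scores (fibre, fat, unsaturated fat) and the RPAQ scores at baseline, one month and three months, following each person's change. Their first stated role is to give context to the qualitative findings. The section then adds: "Descriptive statistics will be reported only. These data will guide in sample size estimations for a later study". That is all it says on how these scores will be summarised.

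The Sample size section gives five patients in each of five practices, "giving a total study sample size of 25", and says openly that no formal calculation was made because this is a feasibility study. Selection of patients allows slightly more per practice: "It is anticipated that five or six invitees will agree to take part".

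On timing, Data collection places the baseline questionnaires first and the tool after them: "Then, in consultation with a health professional in the practice (nurse or general practitioner), they will complete a decision tool". The accelerometer comes later still: "At the end of the initial meeting participants will be invited to wear an Actigraph GT3X accelerometer for a 7 day period". The same section says of activity measurement: "In a definitive study it would be valuable to include an objective measure". The Data analysis section nevertheless labels the two wear periods as follows: "Data derived from the accelerometers (minutes of moderate and vigorous physical activity), at baseline and at the 3-month follow-up point".

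**The concern.** The plan gives the questionnaire data a specific job, sizing a later study, but does not list the outputs that do that job. A sample size for a continuous outcome needs an SD. A baseline-adjusted analysis also needs the correlation between baseline and follow-up. If the report gave only means and SDs at each visit, a later team could work out an interval for each SD but could not recover the correlation, and would have to assume one. With only about 25 people, the estimates are also imprecise, and a reader might take a bare point estimate as firmer than it is.

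The accelerometer raises a related worry. It is a candidate outcome for the definitive study, its SD and correlation are not named either, and its so-called baseline week starts after the tool has been used. The order of activities at the follow-up visits could also be questioned, since the one-month description mentions asking about progress before it mentions the questionnaires.

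At stake is whether the report can serve its stated sizing purpose.

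**Working it through.** **Inputs.** From the documents: 5 practices × 5 patients = 25; at six per practice, 5 × 6 = 30. Assumed, because the documents give no values: 20 complete pairs at three months (loss of five); a correlation r of 0.3 to 0.7, with 0.5 as the central value; normal, independent scores; 95% two-sided intervals.

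**The plan's own figure.** 5 × 5 = 25 reproduces. It is a simple count, with no power calculation behind it.

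**Precision of an SD.** For a fixed target difference, the required N is proportional to SD². With df = n − 1, the 95% limits for N, as multiples of the point value, are df/χ²(0.975, df) and df/χ²(0.025, df). The SD limits are their square roots. For n = 25: 24/39.364 = 0.610 and 24/12.401 = 1.935.

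| n | SD multiple | N multiple |
|---|---|---|
| 20 | 0.76 to 1.46 | 0.58 to 2.13 |
| 25 | 0.78 to 1.39 | 0.61 to 1.94 |
| 30 | 0.80 to 1.34 | 0.63 to 1.81 |

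The only input is n. Naming the SD in the plan, or printing its interval, changes none of these figures. Anyone given an SD and n can calculate the interval.

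**Correlation not reported.** A baseline-adjusted analysis multiplies N by 1 − r². At r = 0.3 this is 1 − 0.09 = 0.91; at r = 0.7 it is 1 − 0.49 = 0.51. The spread is 0.91/0.51 = 1.78-fold.

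**Correlation reported.** Use Fisher's z with SE = 1/√(n − 3), at r = 0.5, where 1 − r² = 0.75.

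- 25 pairs: r from 0.131 to 0.747. N multiple from (1 − 0.747²)/0.75 = 0.588 to (1 − 0.131²)/0.75 = 1.311, a spread of 1.311/0.588 = 2.2-fold.
- 20 pairs: r from 0.074 to 0.772. N multiple from 0.539 to 1.326, a spread of 2.5-fold.

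So a correlation estimated from this sample pins down the later N no better than the assumed range does. The two spreads are not the same kind of quantity (one is a confidence interval, the other a range chosen for illustration), but they show how little precision is at issue.

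**Can the correlation be recovered?** From visit means and SDs alone, no. From individual paired scores, directly. From the SD of change s_d and the two visit SDs s₁ and s₂ in the same people, r = (s₁² + s₂² − s_d²)/(2 s₁ s₂). For example, if all three SDs are equal, r = (1 + 1 − 1)/2 = 0.5. The plan collects the paired scores and intends to look at individual change, so the first route is available to whoever holds the data, and the second to any reader if the SD of change is reported.

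**Would a promised 95% interval be trustworthy?** In simulation at n = 25, the usual chi-square interval for an SD covers 95.0% for normal scores, but 88% at skewness 1.0 and 82% at skewness 1.4 (assumed gamma shapes). Practice clustering matters little: with five practices of five, coverage is 95.0% at an ICC of 0.05 and 94.7% at 0.10. An interval without a stated method would therefore not be a clear gain for a skewed activity score.

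**Timing.** Data collection puts DINE and RPAQ before the tool, so their baseline SDs are untouched by it. The first accelerometer week follows the tool. Both facts can be read from the protocol. The two follow-up visit descriptions list activities without fixing an order, and the three-month description already lists the questionnaires first. Any effect of order on the scores is of unknown size and direction.

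**The case for a change.** The strongest case for a change is that the sizing purpose comes from the protocol itself, so asking which figures serve it is not an outside demand. One sentence committing the team to SDs, numbers of pairs and the correlation would need no extra visits, staff or data, and would fill about one table. A later team working only from a published report with visit means and SDs would lack the correlation.

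The omission stands as a matter of fact, and reporting SDs, numbers of pairs and either the correlation or the SD of change would be good practice. The need for a plan change does not stand. No section says that the team designing the later trial will lack the individual data, and the plan says that this project will inform that trial. The later study's design and primary outcome are not given, so which scores matter for sizing is not yet known. The sizing sentence follows the questionnaire text and comes before the accelerometer sentence, so extending it to accelerometer minutes goes beyond what the plan promised.

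The accelerometer timing is worth a reader's attention: the first week is not a pre-tool measure. That is a labelling note for the report and changes no planned result. A fixed questionnaire order would constrain how follow-up visits open, to guard against an effect that nobody has shown.

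**Conclusion.** No change is needed. The plan leaves a reporting detail open, and analysts preparing a feasibility report would be expected to fill it: SDs and counts are ordinary descriptive statistics, and the paired data allow the correlation or the SD of change to be computed when the later trial is sized.

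The imprecision is real, but it belongs to a sample of 25: a 0.61 to 1.94 multiple on the implied N from the SD, and 0.59 to 1.31 from a correlation of 0.5. Specifying the outputs in advance would remove neither. These figures assume normal, independent scores and complete data; the correlation values are assumptions. The conclusion also assumes that the later trial's designers can use the individual data or a report that gives the SD of change. If only visit means and SDs survived, the cost would be an assumed correlation, worth about 1.8-fold in N over 0.3 to 0.7. Nothing in the documents shows that a later trial would be mis-sized.

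### The accelerometer 'baseline' is recorded in the week after the decision tool, so the study has no objective activity measure from before the tool

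*Combined protocol and SAP*

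**What the plan says.** Data collection sets out the initial meeting in order. Participants first complete DINE and RPAQ with the researcher, "to provide a baseline measure of diet fat and fibre intake and a measurement of physical activity". The tool follows: "Then, in consultation with a health professional in the practice (nurse or general practitioner), they will complete a decision tool". The next contact is then arranged for a month later: "After a shared decision has been made regarding possible changes in diet and physical activity". The last paragraph of that section introduces the device: "At the end of the initial meeting participants will be invited to wear an Actigraph GT3X accelerometer for a 7 day period". Under Follow-up contact, at the 3-month meeting, patients "will be again invited to wear an accelerometer for a 7-day period to record physical activity".

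Data analysis calls the two accelerometer time points baseline and 3 months: "Data derived from the accelerometers (minutes of moderate and vigorous physical activity), at baseline and at the 3-month follow-up point". A few sentences before, it uses the same word for the questionnaires, whose scores are compared "between the baseline measurements and at one month and at 3 months". No earlier wear is described anywhere. Data collection discusses reactivity to wearing the device and accepts it, but does not discuss the order of tool and wear.

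**The concern.** One word covers times on both sides of the intervention. For DINE and RPAQ, baseline is before the tool. For the accelerometer it is the week after a shared decision that may well have been to become more active.

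Objective 3, under Study aims and objectives, is an objective assessment of activity level by accelerometer. If the plan is followed as written, the level reported as baseline includes any early response to the tool, even if no change is ever calculated. Two values labelled baseline and 3 months also invite a reader to subtract one from the other. That difference would omit whatever happened in the first week. It could also appear to contradict the RPAQ change over the same nominal period, for reasons of timing alone. The project is meant to inform the design of a randomised trial, and Data collection says an objective measure of impact would be valuable there, so the label should not be carried forward uncorrected.

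**Working it through.** **Order of events**, from Data collection and Follow-up contact:

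1. DINE and RPAQ (before the tool).
2. Decision tool with the nurse or GP.
3. Shared decision; next contact set for one month.
4. End of the initial meeting: first 7-day wear offered.
5. 3-month meeting: second 7-day wear offered.

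Wear days before the tool: 0 of 7. The activity information from before the tool is RPAQ and, where used for eligibility, the GPPAQ screen. Both are questionnaires.

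**Plan's own figures.** The plan gives no activity level, change or SD, so there is no figure on this point to reproduce. What follows is an illustration with assumed values.

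**Notation.** Let m be the pre-tool level (min/day), d the rise in the first week after the tool, and k the fraction of that rise present at 3 months. Device reactivity is taken as equal in the two wears, so it cancels from the change; it is left out of the level.

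- First wear = m + d
- 3-month wear = m + kd
- True change from before the tool = kd
- Recorded change = (m + kd) − (m + d) = (k − 1)d
- Recorded minus true = (k − 1)d − kd = −d, whatever k is

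**Level**, with m = 20. The error relative to the true level is d/m:

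| d | reported 'baseline' | excess |
|---|---|---|
| 2 | 22 | 2/20 = 10% |
| 5 | 25 | 5/20 = 25% |
| 10 | 30 | 10/20 = 50% |

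**Change**, with d = 10:

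| k | true, kd | recorded, (k − 1)d |
|---|---|---|
| 0.25 | +2.5 | −7.5 |
| 0.5 | +5 | −5 |
| 0.75 | +7.5 | −2.5 |
| 1 | +10 | 0 |
| 1.5 (gradual build-up) | +15 | +5 |

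Results scale with d. At k = 0.5, d = 2 gives +1 true against −1 recorded, and d = 5 gives +2.5 against −2.5. For any d above 0 the sign is reversed for every k strictly between 0 and 1. With d = 0 there is no error.

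**Against RPAQ.** With d = 10 and k = 0.5, an error-free measure taken before the tool and again at 3 months would show +5 where the accelerometer shows −5.

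**The case against.** The strongest reply is that no planned analysis is shown to be wrong. Data analysis specifies comparisons over time for DINE and RPAQ only. For the accelerometer it says just that the two sets of data provide an objective measure. Objective 3 names no time point, the stated reason for using the device here is to test whether its use is feasible, and measuring impact is left to a definitive study. The timing can be worked out from Data collection, and 'baseline' might be meant as a visit label. The text also never says outright that the consultation with the nurse or GP takes place within the researcher's meeting.

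Much of this stands as a limit on the consequence. No formal accelerometer comparison is planned, reporting is descriptive, and m, d and k are assumed. The sentence about guiding later sample sizes follows the questionnaire comparisons, so no sample-size consequence is claimed here. Timing is also not the only reason a questionnaire and a device might disagree.

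It does not rescue the label. The level itself is called baseline when it was measured after the intervention, and the same section uses that word for measurements taken before it. On the order of events, the word 'Then', the next contact a month later and the absence of any separate tool visit all point one way. If another order was intended, Data collection needs to say so, because the label depends on it.

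**Conclusion.** The concern holds. As written, the plan would report a level measured after the tool as the accelerometer baseline, with 0 of 7 wear days before the tool. This rests on reading Data collection as placing the consultation before the end of the initial meeting, which is the natural reading though not stated in so many words.

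The size of the error is d, the unknown first-week rise. It is added to the baseline level and subtracted from any apparent change, the latter if device reactivity is equal in the two wears. The documents cannot say how large d is, and it may be zero. This is a labelling fault that should be corrected. It alters no stated figure, and the planned sample remains 5 × 5 = 25.

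**What to change.** **Sufficient: wording only.** In Data analysis, replace the accelerometer sentence with text to this effect: *Accelerometer minutes of moderate and of vigorous activity will be reported for the first week after the decision tool and for the week after the 3-month meeting, as objective measures at those two times. The difference between them will not be reported as change from baseline, and any SD of change or correlation will be labelled as post-tool to 3 months.* In Data collection, state that the first wear follows the tool. This needs no extra patients, visits or devices.

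**Optional, only if a true objective baseline is wanted.** Complete the first 7-day wear between consent and the tool consultation, and say so in Data collection. The label can then stand. The cost is at least 7 days between consent and the consultation and about one extra contact for each of the 25 planned participants. Any reactivity to the device would then come before the tool. That is a trade-off for the investigators, and the correction does not depend on it.
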